The prevalence of diabetes mellitus (DM) is very high in Spain, being nearly 14% according to oral glucose tolerance test (OGTT) results (1). The management of DM requires a significant consumption of healthcare resources, mainly in relation to the care of vascular complications. Among the late microvascular events which may develop in patients with DM, polyneuropathy (PN) is the most common and disabling, and is the leading cause of morbidity and mortality in these patients (2). Indeed, in Spain, the leading cause of neuropathy is DM, with its prevalence increasing with the presence of DM and other risk factors such as obesity (3).

PN is defined as the presence of symptoms and/or signs of peripheral nerve dysfunction in people with DM after the exclusion of other possible causes (4). The Toronto Panel Consensus on PN defined this disorder as "symmetrical, depending on large fibers, sensory-motor attributable to metabolic and microvessel disorders, as a result of chronic hyperglycemia and other risk factors" (2). In patients with PN, thin fibers (autonomic system - sweating) and thermal and tactile sensitivity are first affected, followed by the involvement of large fibers, presenting an altered vibrating sensation which eventually alters electromyography (EMG) patterns. Therefore, dysfunction of sweat reflex in small distal fibers is one of the earliest changes to be detected in these patients (5).

The most common clinical presentation of PN is distal symmetric polyneuropathy (DSPN), being predominantly sensory in 80% of cases (3). Pain is the most important symptom, being described as burning or flashing, lancinanting, deep, and with frequent exacerbations during rest (4). Pain often affects the quality of life of these patients, and

it is a frequent cause of depression and/or anxiety (6). Moreover, some patients may develop hypoesthesia, which may lead to severe foot lesions (7).

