The prevalence of DSPN varies greatly according to the population, definition and detection method. The Rochester study, including more than 64,000 patients, reported the prevalence of PN to be between 66% and 59% for type1 DM and type 2 DM, respectively (8). The 3rd report of the Technical Study Group of Diabetes of the World Health Organization (WHO) described a prevalence of 40% (8), and 50% in patients with more than 25 years of DM evolution. Pirart *et al.* (9) reported a prevalence ranging from 25 to 48% (7,10-17), while in Spain, Cabezas-Cerrato *et al.* published a figure of 24.1% (11). DSPN-related factors are: age, DM duration, metabolic control, male gender, acute myocardial infarction, hyperlipidaemia (especially hypertriglyceridaemia), smoking, and general cardiovascular risk factors (2,15,16,18). Puig *et al.* (15) also included urinary albumin excretion as a risk factor of presenting DSPN.

The diagnosis of DSPN is commonly made based on signs and symptoms and usually includes the use of several questionnaires such as the Neuropathy Disability Score (NDS), the Neuropathy Symptoms Score (NSS) and the Michigan Neuropathy Instrument (MNI). These questionnaires are easy to perform and are reproducible, sensitive and adequate for use in a screening program (16). Additionally, It was included a short scale (UENS - Utah Early Neuropathy Scale) to screen early neuropathy (17). This sensitive, fast and practical test, has 5 items and their score ranges from 0 to 42 points.

7

There are many confirmatory tests, including measurements of nerve conduction velocity (EMG) and biothesiometry or skin biopsy. However, those most commonly used are the measurement of altered sensations using a vibrating tuning fork with 128 Hz and/or pressure with Semmes-Weinstein 5:07 monofilament (18). Monofilament testing (MFT) is widely accepted and recommended by all scientific societies because of its validity, predictive risk, efficiency and simplicity. Feng *et al.* (19) reported that MFT has a sensitivity of 57-93%, a specificity of 75-100%, a positive predictive value of 36-94% and a negative predictive value of 84-100% compared to the measurement of nerve velocity by EMG. Although electrophysiological measures are more objective and reproducible, they are limited in that they only detect dysfunction based on the presence of thicker and faster (myelinated) fibers and show their involvement later. Consequently, EMG is a specific, albeit very insensitive, test.

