To estimate the validity and performance of a screening test that showed a sensitivity of 82%, a precision of 9% and a confidence interval of 95% (CI95%), considering a loss percentage of 20%, this study will include a total of 160 participants. The proportion of diabetes / prediabetes / normal glucose tolerance will be 2:1:1. The contribution by centres will be: 66% from the Mutua de Terrassa (106 cases) and 34% from Reus (54 cases).

Variables and dynamic data collection:

After verifying the inclusion criteria and receiving written informed consent to participate, during the **first visit** to the Primary Care centres the medical history of the patient will be obtained and a physical examination will be performed using the MFT and the NDS and UENS questionnaires will be given to screen for PN. The patient will also undergo DEC quantification using the Sudoscan® device.

The following variables were collected:

- Age, sex and country of origin.

- Family history of type1 or type2 DM: (yes / no).

- In diabetic population, length of diabetes evolution (in years) since diagnosis.

- Toxic habits: smoking (active smoker / ex smoker / non-smoker); drinking (teetotal, occasional drinker, habitual drinker).

- Other complications of diabetes and year of diagnosis (retinopathy, ischemic heart disease, peripheral vascular disease, cerebral vascular disease and diabetic nephropathy) will be collected from the patient medical records.

- Diabetes treatment.

- Other pharmacological treatments related to: hypotension, hypolipidemia, arterial thrombosis, among others.

On physical examination the following variables will be collected:

- Anthropometric data: Height (cm), weight (kg) (using validated clinical scale with stadiometer in light clothing), waist circumference (cm) (using a flexible measuring tape), measuring the point between the navel and upper iliac crest.

- Systolic/diastolic blood pressure; presence of pulses in pedia/posterior tibial arteries. Blood pressure (mmHg) measurements will be made three times while seated after 30 minutes of rest using a validated automatic device, with each measure being made at least one minute apart. The data recorded will be the mean of the second and third readings.

Other data to be collected include:

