The Chi-square test will be used to analyse qualitative variables and the Student t-test will be performed for quantitative variables. Logistic regression will be used to identify predictors of diabetic neuropathy. Dependent variables (Response) will include the presence of diabetic neuropathy diagnosed by EMG or the NDS / UENS questionnaires. We will compare the performance of DEC with that of the MFT as screening tests of PN.

To determine the validity and reliability of DEC we will calculate the sensitivity, specificity, the positive and negative predictive values, and the positive and negative likelihood ratios. A ROC curve will be used and the area under the curve will be calculated. A p value <.05 will be considered as statistically significant. The analysis will be performed with the statistical packages STATA/SE 12.0 and R for Windows.

LIMITATIONS OF THE STUDY

The main limitation of the present study is accurate diagnosis of diabetic neuropathy since some studies have shown that some cases of diabetic neuropathy present no alterations in the EMG. Indeed, several considerations should be taken into account. Firstly, the EMG test is more specific, albeit not very sensitive, showing positive results in advanced stages of PN. The fingerboard and the NDS questionnaire are commonly used for the diagnosis of diabetic neuropathy, probably because the NDS is carried out prior to EMG and is actually often used to avoid the need for EMG. Therefore, both the EMG and the NDS score, which mainly assess the dysfunction of myelinated fibers provide a good profile for diagnostic confirmation. On the other hand, both the DEC and the MFT are able to diagnose and stage diabetic neuropathy earlier than the previous two tests by the detection of unmyelinated fiber dysfunction. But, another limitation is that MFT is a good test for prediction of a foot ulcer but is certainly insensitive for the detection of early neuropathy. For this reason, we think about the UENS, because of its sensitivity to early sensory loss and ability to record modest anatomic change in sensory function, considering patients with milder neuropathy. Therefore for purposes of simplification and taking into account the possible limitations, we will compare the effectiveness of the measurement of DEC and the use of MFT as diagnostic tools in Primary Care according to whether the true diagnosis is achieved by a) the EMG or b) the score of the NDS or UENS questionnaires.

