Obviously there are another tests to detect early neuropathy, i.e. the Norfolk QOL-DN scale; but this questionnaire is not practical in the clinical scenario. Certainly, this test is a good tool to detect unaware neuropathy in patients with diabetes (24). This study used the Norfolk QOL-DN scale on 25000 patients with diabetes and found 6600 patients who were not aware of their neuropathy nor did their physicians know.

17

Another limitation of this study is the possibility of introducing a selection bias, and thus, we will consecutively include patients with type 2 DM, excluding patients with type 1 DM. We will also include a group of patients without DM or other glucose homeostasis disorders matched by age and gender to a 2:1:1 ratio (80 with DM, 40 with prediabetes and 40 with normal glucose tolerance).

QUALITY ASPECTS

This project will promote a strategy to determine whether the implementation of a new technique simplifies the detection of a major complication of diabetes, such as neuropathy.

Primary Care is clearly the most appropriate setting for the screening of this complication. Indeed, the earlier the diagnosis the better the prognosis. This strategic action on health is directly linked to:

(A) New medical technologies to promote personalized medicine based on the profiles of the individuals and not the disease.

(B) Translational and clinical research, evidence-based scientific and technological knowledge.

(C) Validation of a promising new technology for early detection of diabetic neuropathy in Primary Care.

(D) Application of evidence in clinical practice. This is a validation study of diagnostic technology implemented in real life conditions which would provide additional knowledge for everyday clinical practice.

It is of note that this study will also determine the cost-effectiveness of this new tool which is essential for the validation of new technologies aimed at different healthcare areas such as Primary Care.

Additionally, this project will establish synergies at different levels such as Primary

Care and Neurology, and the results can be shared with a number of centers, primary care areas and different scientific societies involved in the comprehensive care of patients with diabetes.

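### At the event counts this study can expect, ordinary logistic regression judged at p<.05 will exaggerate odds ratios; a short predictor list fixed now and fitted by penalised likelihood would be a cheap improvement

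*Combined protocol and SAP*

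**What the plan says.** The regression gets two sentences under STATISTICAL ANALYSIS. The first gives its purpose: "Logistic regression will be used to identify predictors of diabetic neuropathy". The second gives the responses: neuropathy by EMG, or by the NDS or UENS questionnaire. The only criterion, stated for the analysis as a whole, is "A p value <.05 will be considered as statistically significant". Nothing is said about candidate predictors, who enters the model, selection, the number of parameters, missing values or validation.

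The section on variables and data collection lists what is recorded: demographics, family history, habits, complications, treatments, anthropometry, blood pressure, pulses and laboratory values. One item is limited to part of the sample: "In diabetic population, length of diabetes evolution (in years) since diagnosis". The INTRODUCTION names that item among known risk factors: "DSPN-related factors are: age, DM duration, metabolic control, male gender", followed by myocardial infarction, lipids, smoking, general cardiovascular risk and albumin excretion.

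On size, the plan states "considering a loss percentage of 20%, this study will include a total of 160 participants", split as "80 with DM, 40 with prediabetes and 40 with normal glucose tolerance".

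**The concern.** The sample size was set on the precision of a sensitivity estimate, and no expected event count is given for the regression. With few events, unpenalised logistic regression pushes odds ratios away from 1, and the apparent AUC looks good even when nothing predicts. If candidates are then chosen by looking at p-values, some chance findings will be kept. Duration adds a practical trap: complete-case fitting discards everyone for whom it is blank. What is at stake is the credibility of a published list of neuropathy predictors and their odds ratios.

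**Working it through.** **The plan's own figure.** The sample-size inputs are sensitivity 82%, precision 9% and 95% confidence. n = 1.96² × 0.82 × 0.18 / 0.09² = 70, and 70 / 0.80 = 88 after 20% loss. This does not give 160, which appears only if the 70 are also divided by a prevalence of about 55% that the plan does not state. That is a separate matter; the figures below take 160 as given.

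**Evaluable participants.** 160 × 0.80 = 128 in all; 80 × 0.80 = 64 with diabetes.

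**Expected events**, using the lowest and highest prevalences that the INTRODUCTION gives for Spain and for type 2 diabetes:
- Diabetes group: 64 × 0.241 = 15.4; 64 × 0.59 = 37.8.
- All participants: 128 × 0.241 = 30.8; 128 × 0.59 = 75.5. This applies a diabetic prevalence to people without diabetes, so it is best read as a ceiling.

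At 59% the non-events are the scarcer class (64 − 38 = 26; 128 − 76 = 52), so the upper ends are generous. The protocol calls EMG insensitive, which makes the lower end plausible for that response.

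**Events against variables.** A count of the collected items gives about 30, before dummy coding and without the neuropathy tests. Events per collected variable are 15.4 / 30 = 0.5 to 37.8 / 30 = 1.3 in the diabetes group, and 1.0 to 2.5 over all participants. At the conventional 10 events per parameter (an assumption), 15 to 38 events carry about 1 to 3 parameters, and 31 to 76 about 3 to 7.

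**Bias of the stated method.** I take the unqualified term logistic regression to mean maximum likelihood. Simulations with a true odds ratio of 1.8 per SD (assumed) at these sizes gave:

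| Candidates | ML overstatement of log OR | 1.8 becomes about |
|---|---|---|
| 8 | 10% to 24% | 1.8^1.10 = 1.91 to 1.8^1.24 = 2.07 |
| 15 | 16% to 63% | 1.8^1.16 = 1.98 to 1.8^1.63 = 2.61 |

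Firth-penalised estimates stayed within about 5%. The larger biases belong to the 64-participant settings. The ends of the ranges move by several percentage points with the number of true effects assumed.

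**Selection at p<.05.** With independent null candidates, P(at least one false predictor) = 1 − 0.95^25 = 72% and 1 − 0.95^30 = 79%. For three fixed predictors it is 1 − 0.95^3 = 14%.

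**Apparent discrimination with no signal.** With 25 noise predictors, the apparent AUC averaged about 0.76 to 0.80 in 128 participants (24% to 40% prevalence) and about 0.85 to 0.89 in 64 (40% to 59% prevalence).

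**Would most selected predictors be false?** The table gives the false share after a p<.20 screen and backward selection at .05 from 30 independent candidates (150 runs per setting; effects assumed):

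| Participants / events | 5 true, OR 1.5 | 8 true, OR 1.5 | 8 true, OR 2.0 |
|---|---|---|---|
| 64 / 15 | 57% | 44% | 31% |
| 64 / 38 | 50% | 41% | 27% |
| 128 / 31 | 40% | 32% | 19% |
| 128 / 51 | 39% | 22% | 13% |

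The false share is material throughout, but a majority only with few events and few, weak true effects (or with no true effects at all).

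**Duration.** It is undefined for the 40 + 40 participants without diabetes. An all-participant complete-case model with duration left blank for them keeps 64 of 128. The OGTT is the mirror image, since it is not done in known diabetes; a model with both would have almost no complete cases.

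**The case against.** The strongest reply is that the plan contains no 30-variable model. It names no covariates and no selection procedure; the list is a data-collection list, and p<.05 is a general significance level rather than a selection rule. That is right. A reader might infer that all collected variables, duration included, are model terms; the documents do not say so. The selection figures therefore describe what would happen if the choice were left to the data. The bias figures do not need that assumption, because they arise with 8 candidates and no selection.

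A reader might also infer that glycaemic variables predict the response by construction, because the INTRODUCTION says "PN is defined as the presence of symptoms and/or signs of peripheral nerve dysfunction in people with DM". The operational responses are positivity on EMG, NDS or UENS. The cut-offs given for NDS and UENS are not confined to people with diabetes, and specific objectives 1 and 2 cover prediabetes as well. That inference fails.

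Duration is a coding question: a diabetes-only model, or a suitable code alongside a glucose-group term, avoids the loss. This stands, but the plan does not say which will be done.

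Finally, finding predictors is neither the main objective nor one of the three specific objectives. Sensitivity, specificity, predictive values, likelihood ratios, the ROC analysis and the comparison of DEC with the monofilament do not rest on this regression. That limits the weight of the point.

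**Conclusion.** The point holds as a cheap improvement. On the protocol's own prevalences the regression has about 15 to 38 events in the diabetes group, and at most about 31 to 76 overall. Unpenalised logistic regression judged at p<.05 is a poor tool at that size: log odds ratios are inflated by about 10% to 24% with 8 candidates, and by more with 15. Unplanned selection would very probably add at least one false predictor.

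The tempting stronger conclusion, that most reported predictors would be chance findings, is not supported. The protocol cites established risk factors, and with 31 to 51 events the simulated false share is 13% to 40%.

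The conclusion assumes 20% loss in each group, prevalences carried over from the cited studies, independent predictors, and effect sizes that the plan does not give.

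**What to change.** Replace the regression sentence with a short paragraph that:
- labels the analysis exploratory;
- fixes the predictor list now, from the risk factors named in the INTRODUCTION, with its length set by the expected events;
- states the analysis population;
- fits the model by Firth-penalised likelihood, separately for each response already named (EMG, NDS, UENS);
- reports a bootstrap optimism-corrected AUC;
- enters diabetes duration only in a diabetes-only model, or in an all-participant model with an explicit code for non-diabetics and a glucose-group term, so that nobody is dropped by default.

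Restricting everything to diabetics, imposing a fixed cap of three predictors or dropping NDS is not needed.

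The cost is SAP wording and a little analysis work in R, which the plan already uses; no extra participants or data are required. The downside is that fewer variables can be claimed as predictors.

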Recently developed non invasive techniques are more reproducible and reliable for the detection of early dysfunction of small fibers. One of these new techniques involves the measurement of **dermal electrochemical conductance** (**DEC**) or sudomotor dysfunction index and has been evaluated by well-designed studies (Calvet, Dupin, Winiecki, Black, 2013; Casellini 2013; Devigili 2008; Peltier 2009) which support its use as a screening test (20).

Ramachandran *et al* (21) studied the use of DEC to detect diabetes and other disorders of glucose metabolism. In a study on the use of DEC Casellini *et al* (5) applied a PN test which showed a low sensitivity of 78% and a specificity of 92% in diabetic patients without neuropathy compared to other subjects with neuropathy and a control group. In this latter study, correlation with clinical parameters showed adequate reproducibility of the results, particularly in regard to the measurements of the feet (5). Several other studies (22) also obtained significantly lower DEC values on comparing diabetic patients and controls. In a study of patients following a 12-month program of intense physical activity, Raisanen *et al* (23) observed a greater improvement in DEC compared to weight, waist circumference or maximum oxygen volume (VO₂ max).

Therefore, taking into account the large number of methods used and the learning curve required to correctly implement these techniques as well as the absence of consensus as to which method is the most adequate to diagnose DSPN, the aim of this study is to validate the usefulness of DEC measurement in the early diagnosis of DSPN compared with traditional techniques in the Primary Care setting.

HYPOTHESIS AND OBJECTIVES

The hypothesis of our study is that the measurement of DEC is feasible, sensitive and specific and more or equally effective to other techniques commonly used in the initial screening of diabetic neuropathy in Primary Care.

Main objective

To evaluate the feasibility, effectiveness and performance of a new technique which measures DEC (sudomotor reflex) in the screening of diabetic neuropathy in Primary Care.

Specific objectives

1. Determine the performance of DEC (quantitative assessment of sudomotor reflex) as a tool for the screening of diabetic neuropathy in Primary Care compared with the Semmes-Weinstein 5:07 MFT when an EMG is used to confirm the presence of diabetic peripheral neuropathy in patients with prediabetes and type 2 diabetes.

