2. Determine the performance of DEC (quantitative assessment of sudomotor reflex) as a tool for screening diabetic neuropathy in Primary Care compared with the Semmes-Weinstein 5:07 MFT when the UENS (Utah Early Neuropathy Score) is used to confirm the presence of diabetic peripheral neuropathy in patients with prediabetes and type 2 diabetes.

3. Estimate the cost and cost-effectiveness of the use of DEC in the screening of early diabetic neuropathy in Primary Care.

METHODS

Design

We will perform a blind, prospective study comparing DEC (sudomotor reflex) (Sudoscan®, Impeto Medical, France), EMG, the Semmes-Weinstein 5:07 MFT (10 g), the sensitivity of a vibrating tuning fork 128 Hz, the NDS score and the UENS score in a consecutive series of patients treated in Primary Care.

Sites

The Primary Care teams of Terrassa-Sud and other partners belonging to the Mutua Terrassa reference hospital and those of the University Hospital Sant Joan de Reus reference hospital.

Study subjects

We will consecutively include patients with type 2 DM over 40 years of age, with or without symptoms of neuropathy, attended in Primary Care. We will also include the following two groups of patients matched by age and gender: one including patients with prediabetes (intermediate alterations of glucose metabolism defined as impaired fasting glucose (IFG) and/or impaired glucose tolerance (IGT) determined by OGTT after 2-hour 75 g oral glucose administration and another including patients without glucose alterations (normal glucose tolerance) (control group).

Three main diagnostic categories (normal, pre-diabetes and diabetes) were defined using the WHO criteria based on 2-h postload glucose [<7.8 (140 mg/dL), 7.8–11.0 mmol/L (140-200 mg/dL) and / or fasting plasma glucose (6.1–6.9 mmol/L; 110-126 mg/dL) and >11.1 mmol/L (>200 mg/dL), respectively.

The exclusion criteria are: Type 1 DM, upper or lower limb amputation (except phalanges), diagnosis of neuropathy not related to diabetes, neuropathy by entrapment, use of psychoactive substances, chronic alcoholism, malnutrition; treatment with betablockers, presence of terminal disease or life expectancy less than 3 years. Pregnancy will be ruled out in women (negative pregnancy test) and a possible history of gestational diabetes will also be taken into account.

The study period is from January 1, 2017 to 30 November 2019.

Sample size

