- Blood/urine tests: OGTT (Except in known DM); glycosylated hemoglobin A1c (High Resolution Liquid Chromatography (HPLC)), glomerular filtration rate [Modification of Diet in Renal Disease (MDRD) / Chronic Kidney Disease Epidemiology Collaboration (CKD-EPI)]; lipid profile (total cholesterol, triglycerides and LDL and HDL fractions using the cholesterol oxidase-phenol + aminophenazone (CHOD-PAP) method. These latter parameters should have been determined no more than 6 months previously. If not the determinations should be made in the reference laboratory.

- A score of 8 out of 8 with the Semmes-Weinstein 5:07 MFT(10 g) will be considered as sensitive.

A NDS score greater than or equal to 6 points will be considered as the presence of PN.
A UENS score greater than or equal to 10 points will be considered as the presence of PN.

- The determination of vibration sensitivity will be performed using a 128 Hz Rydel-Seiffer tuning fork. The test will be considered positive for PN when vibration of the tuning fork is not perceived when applied to the thumb or external maleolus.

In the **second visit**, done at the reference hospital, a neurologist blinded to previous test results, will perform neurographyc test including sensory conduction study of the median, ulnar and sural nerves, and motor conduction study of the deep peroneal nerve.

The studied variables will be amplitude of compound muscle action potential and distal latency of the motor nerves, and amplitude and distal latency of sensory nerves. DEC determination and the other neuropathy screening and electrophysiological tests will take no longer than one month.

The **third visit** will be carried out in the Primary Care centre where the results of the previous visit will be recorded and the patient will be informed of the results and the diagnosis.

The cost effectiveness of the different diagnostic methods studied will be evaluated and the incremental cost method to detect new cases compared to traditional methods will be calculated. In addition, a computer simulated model will determine the long term as well as the direct and indirect costs of the different methods.

STATISTICAL ANALYSIS

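### The hypothesis covers the commonly used techniques and the tuning fork is measured, but DEC is compared with the monofilament only, so a favourable result would support only part of the hypothesis

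*Combined protocol and SAP*

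**What the plan says.** The hypothesis, in Hypothesis and objectives, is plural: DEC is "more or equally effective to other techniques commonly used in the initial screening of diabetic neuropathy in Primary Care". The Introduction, discussing confirmatory tests, says that "those most commonly used are the measurement of altered sensations using a vibrating tuning fork with 128 Hz and/or pressure with Semmes-Weinstein 5:07 monofilament".

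The Design paragraph names the tuning fork as one of the tests in the comparison. The data-collection section says "The determination of vibration sensitivity will be performed using a 128 Hz Rydel-Seiffer tuning fork" and gives it a yes/no rule for polyneuropathy.

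The objectives and the analysis use MFT alone:
- Specific objective 1 sets DEC's performance "compared with the Semmes-Weinstein 5:07 MFT when an EMG is used to confirm the presence of diabetic peripheral neuropathy".
- Specific objective 2 sets it "compared with the Semmes-Weinstein 5:07 MFT when the UENS (Utah Early Neuropathy Score) is used to confirm the presence of diabetic peripheral neuropathy".
- Statistical analysis: "We will compare the performance of DEC with that of the MFT as screening tests of PN".
- Limitations ends with the same DEC-MFT pairing and gives simplification as the reason. The same section says that "MFT is a good test for prediction of a foot ulcer but is certainly insensitive for the detection of early neuropathy".

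No stated objective or analysis uses the tuning-fork result. The cost analysis covers the methods studied and compares them with traditional methods, without saying which tests those are.

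**The concern.** The design and the analysis do not match. The hypothesis concerns several techniques, and the design measures at least two that the protocol ranks together as most used, but the analysis tests DEC against one. If DEC does well against MFT, the report can claim equal or better performance than MFT. It cannot claim this against the tuning fork, or against a clinician who uses both tests and acts on either. That second comparison matters most for a primary-care team deciding whether to buy a device. The incremental cost per new case also depends on which tests make up the traditional arm, and this is left open.

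**Working it through.** **1. What the sample size covers.** The plan's only relevant figure is N = 160, from sensitivity 82%, precision 9%, 95% confidence and 20% loss. The usual formula gives 1.96² × 0.82 × 0.18 / 0.09² = 70, and 70 / 0.80 = 87.5, so 88. This does not reproduce 160, which is a separate matter. What counts here is that the inputs describe the precision of one sensitivity. No DEC-versus-comparator difference, margin or power is stated.

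**2. Inputs for the illustration.**
- MFT sensitivity against nerve conduction: 57-93% (Introduction). I use 57% and, as a check, 75%.
- DEC sensitivity: 78% (the DEC study cited in the Introduction) or 82% (the value used under Sample size).
- Tuning-fork sensitivity: not in the documents. Assumed 30-50%.
- MFT and fork conditionally independent among true cases: assumed.

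**3. Sensitivity of MFT or fork positive** = 1 − (1 − Se_MFT)(1 − Se_fork).
- MFT 57%, fork 30%: 1 − 0.43 × 0.70 = 69.9%
- MFT 57%, fork 50%: 1 − 0.43 × 0.50 = 78.5%
- MFT 75%, fork 30%: 1 − 0.25 × 0.70 = 82.5%
- MFT 75%, fork 50%: 1 − 0.25 × 0.50 = 87.5%

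**4. DEC's lead in sensitivity, in points.**

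| MFT | DEC | over MFT alone | over the combination |
|---|---|---|---|
| 57% | 78% | +21 | +8.1 to −0.5 |
| 57% | 82% | +25 | +12.1 to +3.5 |
| 75% | 78% | +3 | −4.5 to −9.5 |
| 75% | 82% | +7 | −0.5 to −5.5 |

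**5. Dependence.** If every case the fork finds is also found by MFT, the combination stays at 57% and the lead stays at 21 or 25 points. Positive correlation puts the answer between that and the table.

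**6. Specificity.** An either-positive rule cannot have higher specificity than either component and will usually have lower. A comparison of sensitivities alone would flatter the combination.

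**7. Precision available.** Losing 20% leaves 64 of 80 with diabetes and 128 of 160 overall. Applying the 40% prevalence quoted in the Introduction gives about 26 cases (0.40 × 64) or, if it held in all three groups, 51 (0.40 × 128). For a paired difference, again under independence, the 95% half-width is 1.96 × √[(ψ − δ²)/cases], where ψ is the discordant proportion and δ the difference. For DEC 82% against a combination at 78.5%, ψ = 0.82 × 0.215 + 0.785 × 0.18 = 0.318 and δ = 0.035. The half-width is about 15 points with 51 cases and 22 with 26.

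**The case against.** The strongest reply is that MFT is a legitimate comparator. The Introduction calls it widely accepted and recommended, and its and/or wording allows monofilament alone to count as common practice. The restriction is also disclosed. This stands as a defence of including MFT. It does not explain leaving out a test that the protocol ranks beside it and already performs. The remedy offered in Limitations, adding UENS, changes the reference standard and not the comparator.

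Four stronger readings are tempting, and the documents do not support them.
- *A win over MFT would not support the hypothesis.* MFT is one of the commonly used techniques, so a win supports that part.
- *The only comparator is the weak one.* Limitations does call MFT "certainly insensitive for the detection of early neuropathy", but it also says that DEC and MFT both detect neuropathy earlier than EMG and NDS. Nothing says the fork is more sensitive. Under the fork values assumed here, MFT is the better single test, and it is the combined rule that makes the harder comparison.
- *Tuning fork and monofilament are the protocol's definition of usual screening.* The Introduction places them among confirmatory tests and describes questionnaires as suitable for screening programmes.
- *Cases that a fork would find will be credited to DEC in the cost analysis.* The text does not say that the traditional methods are MFT alone. It leaves them undefined, and that is the supportable criticism.

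It is also fair to say that more contrasts add multiplicity: two extra comparators against EMG, UENS and NDS would give up to six.

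**Conclusion.** The point holds as a mismatch between hypothesis and design on one side and objectives and analysis on the other. As planned, a favourable result supports only the MFT part of the hypothesis.

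The effect on DEC's apparent advantage is uncertain. It may be nil if the two tests find the same patients. It may be most of the advantage if they find different ones and MFT performs at the bottom of its quoted range. That the lead disappears is not established: with MFT at 57% it reaches zero within the assumed fork range only if DEC is at 78%, and at 82% some lead remains. These figures rest on an assumed fork sensitivity and on conditional independence, and they leave out specificity. The planned data can settle the question; the documents cannot. This is a cheap improvement and not a flaw that invalidates the DEC-MFT comparison.

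**What to change.** - In Statistical analysis, add two secondary paired comparisons: DEC versus tuning fork, and DEC versus MFT or tuning fork positive. Use the positivity rules already given in the data-collection section and the same DEC cut-off as in the DEC-MFT comparison.
- Report differences in both sensitivity and specificity with confidence intervals. Label them secondary and do not rest claims on separate p values.
- Use EMG as the main reference. Where UENS or NDS is the reference, flag the result if vibration testing contributes to the score, since index test and reference then overlap.
- In the cost paragraph, define the traditional methods and include the combined MFT/tuning-fork examination.
- If these comparisons are not wanted, narrow the hypothesis to MFT.

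No extra patients, visits or tests are needed, because the fork result is already collected. The costs are a few more analyses, more secondary contrasts, wide intervals at N = 160, and the possibility that DEC's advantage looks smaller.
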